#### 14.1.2 Definition of Secondary Endpoints

Phase I: Dose-limiting toxicities as assessed by CTCAE version 4 of combination CB-839 and capecitabine in patients with advanced solid tumors with no remaining treatment options or patients for whom single agent capecitabine is an acceptable therapy.

Phase I: Response rate as assessed by RECIST criteria of combination CB-839 and capecitabine chemotherapy in patients with advanced solid tumors with no remaining treatment options or patients for whom single agent capecitabine is an acceptable therapy.

Phase II: Response rate as assessed by RECIST criteria of combination CB-839 and capecitabine chemotherapy in patients with metastatic PIK3CA mutant colorectal cancer who are refractory to fluoropyrimidine based therapy.

Phase II: Overall survival of patients with metastatic PIK3CA mutant colorectal cancer who are refractory to fluoropyrimidine based therapy following treatment with CB-839 and capecitabine chemotherapy. Overall survival is defined as the time from randomization to death from any cause.

#### 14.1.3 Definition of Correlative Endpoints

Phase I: Post-CB-839 pharmacokinetics as assessed by CB-839 drug levels following combination therapy with CB-839 and capecitabine in patients with advanced solid tumors for whom there are no further treatment options or patients for whom single agent capecitabine is an acceptable treatment option.

Phase II: Change in glutaminase activity level as assessed by a glutaminase inhibition assay in both colorectal tumor specimens as well as platelets from patients whom have metastatic PIK3CA mutant colorectal cancer and are refractory to fluoropyrimidine based therapy and who have received treatment with CB-839 and capecitabine chemotherapy.

Phase II: Reduction in nucleotide levels as assessed by HPLC in tumor specimens of patients with metastatic PIK3CA mutant colorectal cancer who are refractory to fluoropyrimidine based therapy and who have received treatment with CB-839 and capecitabine chemotherapy.

Phase II: Change in cellular genome as assessed by whole exome sequencing of tumor specimens of patients with metastatic PIK3CA mutant colorectal cancer who are refractory to fluoropyrimidine based therapy and who have received treatment with CB-839 and

capecitabine chemotherapy.

Phase II: Change in cellular gene expression as assessed by RNA seq of tumor specimens of patients with metastatic PIK3CA mutant colorectal cancer who are refractory to fluoropyrimidine based therapy and who have received treatment with CB-839 and capecitabine chemotherapy.

Phase II: Correlation between plasma trough levels of CB-839 and biomarkers of interest in both tumors and platelets in patients with metastatic PIK3CA mutant colorectal cancer who are refractory to fluoropyrimidine based therapy and who have received treatment with CB-839 and capecitabine chemotherapy.

Phase II: Correlation between clinical response to treatment and biomarkers of interest in patients with metastatic PIK3CA mutant colorectal cancer who are refractory to fluoropyrimidine based therapy and who have received treatment with CB-839 and capecitabine chemotherapy.

## **14.2 Analytic Plan for Primary Objectives**

The phase I component of this study is a dose-escalation trial of CB-839 and capecitabine in patients with advanced solid tumors for whom there are no remaining treatment options or for whom capecitabine is an acceptable treatment. It has been designed to define the recommended phase II dose of CB-839 and capecitabine. A traditional 3+3 dose escalation design will be adopted. Nine to twenty-four patients are expected to be enrolled, depending on the number of dose escalations and assuming that a total of 6 patients will be treated at the final recommended phase II dose level. Patients who complete the first 21 day treatment cycle of CB-839 and capecitabine chemotherapy will be included in the analysis. Patients who do not complete the first 21 day treatment cycle or who fail to receive at least 75% of the doses of both CB-839 and capecitabine for reasons unrelated to toxicity will not be included and must be replaced.

In the phase II component of this study, the primary endpoint is progression free survival rate at 6 months with a null hypothesis of 18% vs. a target of 36%. Employing a 2-stage design, and assuming 80% power and a 0.05 significance level, 40 total patients will be required with 18 in the first stage and the probability of early stopping if the null hypothesis is correct (<3/18 patients with stable disease at 6 months) will be 0.589. If at least 3 patients in 18 has stable disease or better at 6 months, an additional 22 patients will be treated (total of 40 patients). If antitumor activity is identified in the PIK3CA mutant population, we will consider amending the phase 2 trial to assess an additional cohort of patients with wild-type PIK3CA. The statistical considerations will follow the same rules as in the original mutant cohort. Response rate will be determined using RECIST criteria.

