#### **14.5 Sample Size Justification**

The phase I component of the trial will be conducted using a standard 3+3 dose escalation design. As there are four dose levels to be assessed (and two minus dose levels if needed), a total of 9-24 patients will be needed to complete the study.

In the phase II portion of the study, disease control rate is the primary endpoint and the study will be conducted using a Simon two-stage design. As outlined in section 14.2, a minimum of 18 and a maximum of 40 patients will be required.

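### The stage 1 futility rule in 14.2 (fewer than 3 of 18) does not give the stated early-stopping probability of 0.589; that rule gives 0.346, and 0.589 belongs to stopping at 3 or fewer of 18.

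*Combined protocol and SAP*

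**What the plan says.** Section 14.2 sets the phase II primary endpoint as the 6-month progression-free survival rate, with a null of 18% and a target of 36%, "assuming 80% power and a 0.05 significance level". It fixes the size: "40 total patients will be required with 18 in the first stage". Section 14.5 names the method: "the study will be conducted using a Simon two-stage design".

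The stage 1 rule appears twice in 14.2, once for stopping and once for continuing:

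- Stop: "the probability of early stopping if the null hypothesis is correct (<3/18 patients with stable disease at 6 months) will be 0.589".
- Continue: "If at least 3 patients in 18 has stable disease or better at 6 months, an additional 22 patients will be treated".

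The two sentences agree with each other: 0, 1 or 2 successes stop the trial, and 3 or more continue it. Neither 14.2 nor 14.5 gives the number of successes out of 40 needed to call the regimen promising. Neither gives an expected sample size or the attained type I error and power.

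**The concern.** An early-stopping probability is fixed once the stage 1 size, the stopping boundary and the null rate are given, and 14.2 gives all three. The stated 0.589 does not follow from them, but it does follow from a boundary one patient higher. Either the boundary or the probability is wrong, and the documents do not say which was meant.

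This look is the only prespecified efficacy rule that can stop phase II before 22 more patients are treated. Under 4.2.2 each of them must be willing to have a biopsy before and after starting treatment. A reader who relies on 0.589 believes an inactive regimen will more often than not be stopped at 18 patients; under the written rule it will more often go on to 40. Section 14.2 also says that a possible PIK3CA wild-type cohort would follow the same rules, so the error would carry over.

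**Working it through.** **Inputs (all from 14.2).** Null rate p0 = 0.18, target p1 = 0.36, stage 1 size n1 = 18, total n = 40 (22 in stage 2), significance level 0.05, power 80%, stated early-stopping probability 0.589.

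**Stage 1 under the null.** Let X1 ~ Bin(18, 0.18), with P(X1 = x) = C(18, x) · 0.18^x · 0.82^(18−x).

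| x | P(X1 = x) | P(X1 ≤ x) |
|---|---|---|
| 0 | 0.0281 | 0.0281 |
| 1 | 0.1110 | 0.1391 |
| 2 | 0.2071 | 0.3462 |
| 3 | 0.2425 | 0.5888 |

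- The plan's figure is reproduced by stopping at 3 or fewer: P(X1 ≤ 3) = 0.5888, or 0.589.
- The written rule stops at 2 or fewer: P(X1 ≤ 2) = 0.346.
- The gap is P(X1 = 3) = 0.243, about 24 percentage points.
- For the written rule to give 0.589, the null rate would have to be about 12.8%.

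**Expected sample size under the null**, 18 + 22 × (1 − early-stopping probability):

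- Written rule: 18 + 22 × (1 − 0.3462) = 32.4.
- Stop at 3 or fewer: 18 + 22 × (1 − 0.5888) = 27.0.

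**Type I error and power.** Let r1 be the largest stage 1 count that stops the trial and c the number of successes out of 40 needed to declare activity. The probability of declaring activity is the sum over x from r1 + 1 to 18 of P(X1 = x) · P(X2 ≥ c − x), with X2 ~ Bin(22, p). It is evaluated at p = 0.18 for type I error and at p = 0.36 for power. The plan gives no c, so several were tried:

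| r1 | c (of 40) | Type I error | Power |
|---|---|---|---|
| 2 (written) | 11 | 0.0892 | 0.896 |
| 2 (written) | 12 | 0.0439 | 0.826 |
| 2 (written) | 13 | 0.0195 | 0.729 |
| 3 | 11 | 0.0814 | 0.869 |
| 3 | 12 | 0.0415 | 0.807 |
| 3 | 13 | 0.0188 | 0.717 |

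With either stage 1 boundary, only c = 12 meets both the 0.05 level and the 80% power. This reads 0.05 as one-sided, as is usual for a Simon design; 14.2 does not state sidedness.

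**Which design lies behind 0.589.** Two-stage designs with total sizes from 25 to 55 were searched at 18% versus 36%, with type I error at most 0.05 and power at least 0.80. Among those with n = 40, the one with the smallest expected sample size under the null (27.05) has n1 = 18, stops at 3 or fewer, and declares activity at 12 or more. It matches the plan's 18, 40 and 0.589 together. It is not the best design over all sizes: the search also finds an expected size of 23.9 at n = 47 and a smallest maximum of 36. The identification therefore rests on the three matching figures.

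**The case against.** The mismatch itself has no good defence. A lost 'or equal' sign in the stopping phrase cannot explain it, because the continuation sentence puts the same boundary in words. The case on the other side concerns how much it matters and which part is wrong.

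- **The rule can be carried out and error control holds.** The stop and continue sentences are consistent. With 12 of 40 as the cutoff, the written rule has type I error 0.044 and power 0.826. It is also less likely to stop wrongly when the true rate is 36%: P(X1 ≤ 2) = 0.019, against P(X1 ≤ 3) = 0.066. This stands. The damage is to the futility protection and to the truth of a reported operating characteristic, not to the false-positive rate.
- **The intended boundary is inferred.** The documents nowhere say that 3 of 18 should stop the trial; only the probability points there. This also stands, and is why two repairs are offered.
- **Moving the boundary is more than an edit.** The Summary of Changes introduces the 18-and-40 design in its 12/16/2020 entry, and the documents do not show whether stage 1 outcomes are already known. If they are, changing the boundary would be data-dependent. This limits which repair is open.
- **The sponsor can end the study at any time under 6.6.** That is a general power, not a prespecified efficacy rule, and it does not make 0.589 correct.

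**Conclusion.** The concern holds. The mismatch follows from exact arithmetic on the plan's own figures and depends on no choice of sidedness, approximation or software. The expected sample sizes are also exact, though the plan states neither of them. The type I error and power figures rest on two assumptions that the plan does not state: a cutoff of at least 12 of 40 and a one-sided 0.05 level.

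This must be fixed. The go/no-go rule of the primary analysis contradicts its own stated probability, and a 3 of 18 result, which about one null trial in four would produce, would leave the decision open to dispute.

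**What to change.** Reconcile rule and probability in 14.2, by one of two routes:

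1. **Keep 0.589.** Stop if 3 or fewer of 18 are successes, and continue to 40 if 4 or more. With success at 12 or more of 40, report type I error 0.0415, power 0.807 and expected sample size under the null 27.0.
2. **Keep the written rule.** Change the early-stopping probability to 0.346. With success at 12 or more of 40, report type I error 0.044, power 0.826 and expected sample size under the null 32.4.

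Under either route, state the cutoff of 12 of 40 and that the 0.05 level is one-sided. Route 1 is open only if stage 1 outcomes are not yet known. If they are, keep the boundary on record, correct the probability, and say when the correction was made.

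In the same edit, define the event counted as a success. Section 14.2 names the 6-month progression-free survival rate but counts stable disease or better at 6 months. Section 14.5 calls the primary endpoint disease control rate, and section 12.0 calls it response rate. The boundaries above apply to whichever binary endpoint the 18% and 36% describe.

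The cost is a short amendment to 14.2. The maximum of 40 does not change and no extra patients are needed.

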## **14.3 Analytic Plan for Secondary Objectives**

All toxicities will be summarized as the percentage of patients experiencing each type and grade of event according to dose level. Patients who receive at least one dose of treatment will be included in the analysis.

In the phase I portion of the study, response rate will be summarized using frequencies and proportions by dose level. Response to treatment will be determined using RECIST criteria.

#### **14.4 Analytic Plan for Correlative Objectives**

All correlative studies will be performed in biospecimens from the intent to treat population of 18-40 patients from the phase II portion of the study. Pre- and post-treatment tumor samples from the same patients will be used for assessments, except glutaminase activity, which will be performed on post-treatment samples only (tumor samples and platelet samples). All correlative continuous measurements will be summarized using mean +/- SEM, range and median; all categorical measurements will be summarized using frequencies and proportions. Change in these measurements in tumors before and after therapy will be assessed using paired Wilcoxon tests. Unpaired Wilcoxon tests will be used for assessment of glutaminase activity in post-treatment samples only. Assuming a maximum of 40 patients (2-sided test with 0.05 significance level and 80% power), for the paired T-test we can detect normalized differences of 4.5 to 18.2% for standard deviations of the difference between pairs ranging from 0.10 to 0.40. Correlations of plasma trough levels and platelet glutaminase activity will be calculated using Spearman correlation coefficients. Assuming a maximum of 40 patients, 2-sided test with 0.05 significance level, we have >98% power to detect a Spearman correlation coefficient of 0.60 or higher.

Whole exome sequencing and RNA sequencing will be performed on pre and post treatment tissue samples and compared for differences for all patients (n=40 patients maximum). All of these analyses are exploratory, hence no power calculations are shown.

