### 2.3 **Correlative Objective(s)**

#### 2.3.1 Phase II

To determine the change in glutaminase activity level in tumor specimens and platelets following treatment with CB-839 and capecitabine chemotherapy in patients with metastatic PIK3CA mutant colorectal cancer who are refractory to fluoropyrimidine based therapy.

To determine the reduction in nucleotide levels in tumor specimens following treatment with CB-839 and capecitabine chemotherapy in patients with metastatic PIK3CA mutant colorectal cancer who are refractory to fluoropyrimidine based therapy.

To determine genomic changes in both DNA and RNA in tumor specimens following treatment with CB-839 and capecitabine chemotherapy in patients with metastatic PIK3CA mutant colorectal cancer who are refractory to fluoropyrimidine based therapy.

To determine the correlation between plasma trough levels of CB-839 and biomarkers of interest in patients with metastatic PIK3CA mutant colorectal cancer who are refractory to fluoropyrimidine based therapy and who have received treatment with CB-839 and capecitabine chemotherapy.

To determine the correlation between clinical response to treatment and biomarkers of interest in patients with metastatic PIK3CA mutant colorectal cancer who are refractory to fluoropyrimidine based therapy and who have received treatment with CB-839 and capecitabine chemotherapy.

To generate organoids from patient tissue biopsies obtained prior to and following treatment in patients treated with CB-839 and capecitabine chemotherapy in patients with metastatic PIK3CA mutant colorectal cancer who are refractory of fluoropyrimidine based therapy.

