## 10.0 CORRELATIVE STUDIES

### 10.1 Glutaminase Activity Level

The purpose of assessing the change in glutaminase activity level is to determine if administration of CB-839 results in a decrease in glutaminase activity in post-treatment platelets and biopsy specimens as compared to prior to CB-839 treatment using a glutaminase inhibition assay.

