#### 10.1.2 Rationale for Analysis

Demonstration of glutaminase inhibition in both platelets and tumor specimens following treatment with single agent CB-839 as compared to prior to initiation of treatment will provide a pharmacodynamic marker indicating that CB-839 is reaching its intended target. If correlation is seen between platelets and tumor specimens in regard to level of inhibition, it may be necessary to assess platelets only in regard to glutaminase inhibition in subsequent studies. See section 14.4 for statistical plan.

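### The glutaminase endpoint is a change from before treatment, but Section 14.4 assays post-treatment samples only, does not say how a change is derived, and uses an unpaired test with no named groups

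*Combined protocol and SAP*

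**What the plan says.** Four places describe a comparison with the pre-treatment state.

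- Section 2.3.1, objective: "To determine the change in glutaminase activity level in tumor specimens and platelets following treatment with CB-839 and capecitabine chemotherapy".
- Section 14.1.3, endpoint: "Change in glutaminase activity level as assessed by a glutaminase inhibition assay in both colorectal tumor specimens as well as platelets".
- Section 10.1, purpose: to learn whether CB-839 "results in a decrease in glutaminase activity in post-treatment platelets and biopsy specimens as compared to prior to CB-839 treatment".
- Section 10.1.2, rationale: inhibition in both tissues "as compared to prior to initiation of treatment will provide a pharmacodynamic marker indicating that CB-839 is reaching its intended target".

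The analysis plan takes a different line. Section 14.4 uses tumor samples from before and after treatment, "except glutaminase activity, which will be performed on post-treatment samples only (tumor samples and platelet samples"). Footnote c of the phase II calendar (Section 11.4) sets the same limit for blood and tissue, and Section 10.1.6 sets it for tumor.

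On tests, Section 14.4 says "Change in these measurements in tumors before and after therapy will be assessed using paired Wilcoxon tests" and then "Unpaired Wilcoxon tests will be used for assessment of glutaminase activity in post-treatment samples only".

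The phase II Study Schema, the Protocol Summary (Interventions) and Section 3.2 (phase II design) obtain both baseline and day 10-15 blood and tissue, and give glutaminase activity as a reason for doing so. Section 10.1.3 collects platelets at the pre-treatment biopsy and again at day 10-15.

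**The concern.** A change needs two values per patient or a defined reference. Section 14.4 supplies one value and no reference, so a stated rule of the analysis plan defeats a stated endpoint. The test assigned to the single value compares two independent groups, but phase II is single arm and no grouping is given. Whatever grouping is chosen, the test would show whether post-treatment activity differs between groups, not whether activity fell.

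Section 10.1.2 treats inhibition relative to pre-treatment as the evidence that the drug reaches its target. If the efficacy result is negative, this endpoint helps to separate a drug that did not inhibit glutaminase from a drug that did so without clinical benefit. Post-treatment levels alone do not make the comparison that the plan describes.

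**Working it through.** **1. Sections side by side**

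| Place | What it requires for glutaminase |
|---|---|
| 2.3.1, 14.1.3 | Change, in tumor and platelets |
| 10.1, 10.1.2 | Comparison with before treatment, both tissues |
| Phase II Schema, Protocol Summary, 3.2 | Baseline and day 10-15 blood and tissue, for this assay |
| 10.1.3 (platelets) | Blood collected at both times |
| 11.4, pharmacodynamic row and footnote c | Pre-treatment column marked, platelets drawn on the biopsy day, but only post-treatment specimens assayed |
| 10.1.6 | Tumor: post-treatment biopsy only. Platelets: describes the day 10-15 draw |
| 11.2.1 | Lists the baseline biopsy, no platelet draw |
| 14.4 | Both tissues: post-treatment only, unpaired test |

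Collecting baseline blood without assaying it would reconcile 10.1.3 with 11.4 and 14.4. It would not reconcile the Schema, the Protocol Summary and 3.2, which say the baseline samples are for this assay, nor the change endpoint itself.

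**2. Pairs available.** A pair needs an assayed value before and after treatment. Under 14.4 the number assayed before treatment is 0 in each tissue, so there are 0 pairs out of at most 40. The paired sentence in 14.4 is also confined to tumors, so platelets would have no paired test even if their baseline were assayed.

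**3. The plan's own figure.** Inputs from 14.4: n = 40, two-sided 0.05, 80% power, SD of the paired difference 0.10 to 0.40. For the paired t-test, solve for d such that a noncentral t with 39 degrees of freedom and noncentrality d√40 gives 80% power: d = 0.454.

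- SD 0.10: 0.454 × 0.10 = 0.045, or 4.5%.
- SD 0.40: 0.454 × 0.40 = 0.182, or 18.2%.

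Both figures reproduce. They need two values per patient, so they do not cover glutaminase as 14.4 now stands.

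**4. What pairs would give.** For the signed-rank test (exact null, 40,000 simulated runs, normal differences, two-sided 0.05):

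- 40 pairs: power 0.810 at 0.47 SD of the paired differences.
- 18 pairs, if phase II stops after stage one: power 0.80 at 0.72 SD.

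**5. The unpaired test.** With no groups named, its power cannot be computed. These are illustrations under assumed groups, with normal data, equal variance and 80% power:

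- 40 patients split 20/20: about 0.94 between-patient SD (rank-sum, simulated).
- 40 patients split 7/33: 1.20 SD by t-test, about 1.23 SD for the Wilcoxon test after dividing sample sizes by π/3.
- 40 values against 40 values, treated as independent: 0.63 SD by t-test, about 0.65 SD for the Wilcoxon test by the same adjustment.

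The SD here is between patients, and the question is association with a group. These figures are therefore not comparable with step 4.

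**The case against.** The strongest reply is that the endpoint names an inhibition assay, which may give percent inhibition from one post-dose sample against an uninhibited reference. Section 10.1.6 refers the method to a laboratory manual that is not among the documents, and Section 1.2.3 reports inhibition in five on-treatment tumor specimens without mentioning baseline tumor. This stands as far as it goes: a reader might infer that change cannot be measured in this trial, and the documents do not support that. They support only that the plan does not say how. A within-sample reference would still not be the pre-treatment comparator of Sections 10.1 and 10.1.2. For platelets, Section 1.2.3 describes earlier studies that assessed blood at baseline and four hours after dosing.

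A second reply is that the baseline platelet draw is settled. Largely it is. A reader might infer from Sections 10.1.6 and 11.2.2 that the draw is denied, but the first describes the assayed sample and the second is a day 10-15 list. The Schema, the Protocol Summary, Section 3.2, Section 10.1.3 and the marked calendar column all collect it. What remains is mainly its omission from the Section 11.2.1 screening list.

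A third reply is that responders versus non-responders is the natural grouping, given the objective "To determine the correlation between clinical response to treatment and biomarkers of interest". That is reasonable, but Section 14.4 does not say it, and such a test answers that objective and not the change objective.

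**Conclusion.** The point holds as a specification defect. Following Section 14.4 exactly yields no pre/post glutaminase pairs in either tissue, and the comparison stated in Sections 10.1 and 10.1.2 cannot then be made. The arithmetic in Section 14.4 is correct for 40 pairs; the error would be to read it as covering this endpoint.

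A reader might also take the 0.94 SD of an equal 20/20 split as the best any unpaired test could achieve. The documents do not support that. Section 14.4 names two post-treatment sample types, and a 40 versus 40 comparison of them would detect about 0.65 SD. That comparison would be questionable, because the values come from the same patients and may be on different scales, but with no groups named it cannot be excluded. The figure is an illustration, not a bound.

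The effect is confined to one correlative endpoint. The primary endpoint, the sample size and the nucleotide analysis are untouched, and so is the correlation of trough level with platelet activity, which can use post-treatment activity. The conclusion rests on the current text and on the laboratory manual not having been seen. The change should be made, but it is not critical to the trial.

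**What to change.** 1. **Platelets.** Assay the baseline sample that Section 10.1.3 collects and the Section 11.4 calendar marks. Add the draw to the Section 11.2.1 list, amend footnote c, and extend the paired Wilcoxon sentence in Section 14.4 to platelets. If baseline platelets cannot be assayed, restate the platelet endpoint as post-treatment activity.
2. **Tumor.** First reconcile the core counts: Section 10.1.3 takes four cores but labels three vials, and Section 10.4.3 takes three cores. The second frozen specimen is the reserve for low nucleic-acid yield or necrosis, so assay baseline frozen tissue only where enough remains after that use. Report the number of pairs and why others are missing, since pairs determined by tissue yield may be selected. Otherwise restate the endpoint as post-treatment activity, or as percent inhibition with its within-sample reference defined, and align Sections 10.1, 10.1.2 and 14.1.3.
3. **Unpaired test.** Name the groups (for example responders versus non-responders, for the response-biomarker objective) or drop the test. Label any detectable difference quoted for it as illustrative.
4. **Consistency.** Make the Study Schema, the Protocol Summary and Sections 3.2, 10.1.6, 11.4 and 14.4 say the same thing about what is drawn and what is assayed.

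The cost is up to 40 extra platelet assays on samples already collected under the protocol, plus tumor assays where tissue allows. Any patient already treated without the baseline draw cannot be recovered. Restating an endpoint costs only text but gives up the pre-treatment comparison. No new biopsies or patients are needed.
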